CLINICAL STUDY PROTOCOL

Protocol Title

**Effect of Culturally Tailored Diabetes Education on Self-Management Behaviors of
Adult Hispanic Males with Type 2 Diabetes Mellitus**

Protocol Version

10/21/2025

version 3.0

Study Personnel

PI: [name], MSN, RN, NP-C
Program Director, HMH Plainfield Health Connections
PhD Candidate, Wilkes University, Passan School of Nursing
[contact]
[contact]

Sub-I(s): [name], DNP, APN, PMHNP-BC, RPYB, NE-BC
Nurse Scientist, Ann May Center of Nursing Research, HMH
[contact]
[contact]

Statistical support: N/A

Protocol Development support: N/A

Name and information of sponsor: Hackensack Meridian *Health*

Research Location:

Hackensack Meridian Health, JFK University Medical
Center Plainfield Health Connections
[name]

Revision#	Version Date	Summary of Changes	Consent Change (Y/N)
Original version 1.0	TBD	N/A	N
Version 2.0	6/2/2025	Informed consent, privacy & confidentiality, ethical considerations, data usage & storage all updated.	N
Version 3.0	10/21/2025	Protocol & consent revised to reflect addition of hybrid sessions.	Y

Summary

Study Title	Effect of Culturally Tailored Diabetes Education on Self-Management Behaviors of Adult Hispanic Males with Type 2 Diabetes
Study Design	Quasi-Experimental Quantitative Design
Primary Objective	To evaluate the effect of culturally tailored diabetes education on self-management behaviors of Hispanic males, aged 18-64, with type 2 diabetes mellitus (T2DM).
Secondary Objective	N/A
Research Intervention(s)	Five weeks of culturally tailored diabetes self-management education modeled after Association of Diabetes Care and Education Seven-item Framework (ADCES7).
Study Population	Adult Hispanic Males, aged 18-64 years diagnosed with Type 2 Diabetes Mellitus (T2DM)
Sample Size	Up to 98 based on power analysis and attrition rate

Study Duration for Participants	10 hours (Educational sessions: 120 minutes over 5 weeks)
--	---

1 – Introduction

Diabetes mellitus (DM) is a global public health concern. In the United States, adult Hispanic males are particularly vulnerable to type 2 diabetes mellitus and are more likely to develop complications and subsequently die from it, compared to non-Hispanic White males. Evidence suggests good self-management behaviors can potentially prevent disease-related complications and improve clinical outcomes. The American Diabetes Association and Association of Diabetes Care and Education Specialists have endorsed diabetes self-management education as a necessary component of care for all individuals living with the disease. However, adult Hispanic males with type 2 diabetes mellitus living in the Middle Atlantic Region of the U.S., especially those who are underserved, typically lack access to formal diabetes self-management education (DSME). Further, the majority have never participated in such educational activities (Au et al., 2021; New Jersey Department of Health, 2013; 2017; 2023). A large body of evidence suggests DSME can effectively improve self-management behaviors in diverse populations around the globe (Abraham et al., 2020; Dietz et al., 2022; ElGerges, 2020; Gehlawat et al., 2019; Hailu et al., 2019; Jiang et al., 2022; Leong et al., 2022; Oluchina, 2022; Riangkam et al., 2022; Tamiru et al., 2023; Yu et al., 2022; Zheng et al., 2019). However, this author identified a gap in the literature as to its effectiveness among adult Hispanic males. The purpose of the proposed study is to examine the effect of culturally tailored diabetes education on self-management behaviors of adult Hispanic males, aged 18-64 years, with type 2 diabetes mellitus living in the Middle Atlantic Region of the U.S. This study can shed more light on the effectiveness of community-based, culturally tailored diabetes educational activities in this vulnerable population and guide future efforts towards enhancing self-management.

2 – Background

2.1. Background/Literature Review

Diabetes mellitus is a global health problem and a major driver of disability and death worldwide (Global Burden of Diseases, Injuries, and Risk Factors Study [GBD] 2021 Diabetes Collaborators, 2023; International Diabetes Federation [IDF], 2021; Khan et al., 2020; World Health Organization [WHO], 2023). With over 500 million cases (roughly 6% of the world's population), DM has been labeled one of the most rapidly evolving public health crises of the Twenty-First Century. From 1990 to 2021, prevalence rose by over 90% globally, from 3.2% to 6.1%, and is expected to rise above 7.0% by 2030 (approximately 700 million cases. Internationally, more than six million deaths (1 every 5 seconds) were

attributed to DM or related complications in 2021 alone ([GBD] 2021 Diabetes Collaborators, 2023; IDF, 2021; Khan et al., 2020; U.S. Census Bureau, 2023; WHO, 2023).

The high cost of care associated with DM places great economic and financial constraints on individuals, families, healthcare systems, and society at large (American Diabetes Association [ADA 2023]; IDF, 2021). Globally, it is estimated that over \$960 billion was spent on DM care in 2021 with projected spending to exceed \$1 trillion by 2030 (IDF, 2021). Diabetes Mellitus is currently the costliest chronic medical problem in the U.S. with \$1 in every \$4 of healthcare costs being attributed to clinical management (ADA, 2023; Centers for Disease Control and Prevention [CDC], 2022a). The ADA (2023) estimates that persons diagnosed with DM in the U.S. spend more than twice of those without.

Serious complications can develop from DM, resulting in disability or even death (CDC, 2022c; IDF, 2021; WHO, 2023). Damage to major organs and lower extremities can occur (CDC, 2022c), including ischemic heart disease and stroke, the number one and two contributors to the global disease burden, respectively (GBD 2021 Diabetes Collaborators, 2023). In the U.S., the CDC (2022a) has estimated that persons with DM are two times more likely to develop heart disease and/or have a stroke, compared to those without.

Hispanic Americans have a greater than 50% chance of developing type 2 diabetes mellitus (T2DM), and at a much earlier age (CDC, 2022b). The U.S. Department of Health and Human Services Office of Minority Health (2021) has estimated that Hispanic males 18 years and over, were more likely to receive a diagnosis of T2DM, be admitted due to poorly controlled disease, develop visual problems, undergo amputations, or die prematurely from the disease or its complications, compared to non-Hispanic White males.

Diabetes is essentially a self-managed disease. Self-management behaviors are daily activities performed to reduce disease burden on overall health (ADA, 2023; Association of Diabetes Care and Education Specialists [ADCES], 2021; Powers et al., 2021). These include activities such as glucose monitoring, healthy eating, staying active, taking medication, and foot care. Self-management behaviors are typically carried out by individuals with support from family and loved ones. Diabetes educational activities that embody these concepts have been reported to enhance self-management, improve clinical outcomes, and delay onset of complications. Therefore, such activities have been endorsed as a critical aspect of care for all persons living with T2DM (ADA, 2023; ADCES, 2021; Powers et al., 2021).

When tailored to the culture of the target population, diabetes education can significantly improve self-management behaviors, increase knowledge, and improve outcomes, particularly among those with T2DM living in underserved communities (Brown et al., 2021; Gehlawat et al., 2019; Tamiru et al., 2023). Culturally tailored diabetes education has also been shown to decrease the cost of diabetes-related care, reduce emergency room visits, and

inpatient admissions (ADCES, 2021; CDC, 2019). However, little is known about its effect on adult Hispanic males living with the disease. Therefore, this study aims to evaluate the effect of culturally tailored diabetes education on self-management behaviors of adult Hispanic males, aged 18-64, with T2DM, living in the Middle Atlantic Region of the United States.

3 – Rationale, Objectives and Hypotheses

3.1. Study Rationale/Problem Statement/Research question or Study significance

Evidence shows that culturally tailored diabetes self management education can significantly improve DM outcomes, however, little is known about its impact among adult Hispanic males with T2DM, which this study aims to address.

3.2. Hypotheses

Research Hypotheses for the proposed study are as follows:

H₁ – Five weeks of culturally tailored diabetes education will have a statistically significant effect on **diet scores** of adult Hispanic males with T2DM post-intervention.

H₂ – Five weeks of culturally tailored diabetes education will have a statistically significant effect on **exercise scores** of adult Hispanic males with T2DM post-intervention.

H₃ – Five weeks of culturally tailored diabetes education will have a statistically significant effect on **medication scores** of adult Hispanic males with T2DM post-intervention.

3.3. Primary Objective

To evaluate the effect of culturally tailored diabetes education on self-management behaviors of adult Hispanic males, 18-64, with T2DM.

3.4. Primary Outcome Variable

Title: Diabetes Self-Management (DSM) Behaviors

Description: DSM will be measured by self-reported data on diet, exercise, and medication adherence, utilizing scoring derived from the Spanish version of the Summary of Diabetes Self-Care Assessment (SDSCA-Sp) scale. SDSCA-Sp core items measure participants' DSM activities during the past seven days. In case of sickness during that period, participants are asked to respond based on the last seven days they were not sick.

Scoring: Scores will be calculated separately for each subscale of the instrument. Number of days per week an activity is performed, on a 0–7 scale, is recorded, with higher numbers corresponding to higher levels of self-care activity performance (Toobert et al., 2000; Vincent et al., 2008).

Primary Outcome Measure 1**Title:** Healthy Eating**Description:** Healthy eating behaviors will be measured by self-reported data on diet adherence utilizing scoring derived from the SDSCA-Sp scale.**Scoring:** Items 1–5 relate to dietary behaviors, for example, “how many of the last seven days have you followed a healthful eating plan?” Diet will be scored using the mean number of days for items 1-5, using a reverse score for item 4 (Toobert et al., 2000; Vincent et al., 2008).**Primary Outcome Measure 2****Title:** Staying Active**Description:** Physical activity behaviors will be measured by self-reported data on exercise adherence utilizing scoring derived from the SDSCA-Sp scale.**Scoring:** Items 6–7 pertain to exercise activity, for example, “on how many of the last seven days did you participate in at least 30 minutes of physical activity?” Exercise will be scored using the mean number of days for items 6 and 7.**Primary Outcome Measure 3****Title:** Medication Use**Description:** Medication use behaviors will be measured by self-reported data on medication adherence utilizing scoring derived from the SDSCA-Sp scale.**Scoring:** Medication use will be scored using total number of days for item 12.**Timeframe:** Self-reported data will be collected at Week 1 (baseline) and Week 5 (following implementation of educational sessions). The timeframe of instrument completion is 45-60 minutes.**3.5. Secondary Objective(s)**

N/A

3.6. Secondary Outcome Variable(s)/Measure(s)**Secondary Outcome Measures**

N/A

3.7. Exploratory objective(s)

N/A

3.8. Exploratory outcome variable(s)

N/A

Exploratory outcome measure 1

N/A

4 - Study Design**4.1 General Design**

A one-group, pretest-posttest, quasi-experimental design (Gray et al., 2017) will be used for this study. This quantitative interventional design was chosen because the study will not have a control group and there will be no random assignment or random selection of participants. However, the independent variable of C-DSME will be manipulated and the outcome variable of DSM behaviors will be measured before and after the intervention for comparison (Gray et al., 2017). Participation in the research study is a requirement to participate in the educational sessions.

4.1.1 Study Duration

12-18 months

4.1.2 Participant Duration

10 hours over the course of 5 weeks

4.1.3 Number of Study Sites

Single site study - HMH JFK University Medical Center Plainfield Health Connections

4.2 Study Population

Adult Hispanic males, aged 18-64, diagnosed with type 2 diabetes mellitus

4.2.1. Number of Participants

98 participants, based on *a priori* power analysis and approximately 50% incompleteness rate to counter attrition.

4.2.2. Eligibility Criteria**Inclusion Criteria:**

The inclusion criteria will be:

1. **Age:** Adult Hispanic males 18-64 at time of study intervention.
2. **Diagnosis Codes:** Patients with self-reported diagnosis of T2DM without complex, co-morbid conditions such as severe kidney disease and terminal illnesses such as cancer.
3. **Payor:** N/A

4. **Procedure Codes:** N/A
5. **Medications:** N/A
6. **Test/Lab results:** N/A
7. **Study site:** HMH JFK University Medical Center Plainfield Health Connections
8. **Service:** Outpatient/Inpatient
9. **Date Range:** N/A
10. **Communication:** Subjects identified with a language barrier who agree to receive HMH medical interpreter services.

Exclusion Criteria:

The exclusion criteria will be:

1. **Age:** Hispanic adult males over the age of 65 years, children, adolescents, and females.
2. **Diagnosis Codes:** Hispanic males aged 18–64 with T2DM and complex, co-morbid conditions that can impair ability to perform self-care activities. This includes those with cancer and other terminal illnesses; severe cardiovascular and cerebrovascular diseases, such as congestive heart failure; severe kidney disease; physical disability; cognitive impairment; and major psychiatric disorders like schizophrenia.
3. **Payor:** N/A
4. **Procedure Codes:** N/A
5. **Communication:** Potential participants with an identified language barrier who refuse to receive HMH medical interpreter services.

4.2.3. Vulnerable Populations

- Minority individuals are considered as a vulnerable group when it comes to access to healthcare services (Aguayo-Mazzucato et al., 2019). The culturally tailored diabetic self management educational intervention will be applied to all participants meeting inclusion criteria.
- A certified medical Spanish interpreter (HMH certified) will be present during all participant encounters to ensure that information presented is language appropriate.
- Informed consent will be obtained from each participant at the time of recruitment; approximately 30-45 minutes will be given for questions.

4.3 Withdrawal Criteria

Participants may choose to withdraw from the study at any time.

- Study participants are required to participate in 80% of educational sessions. Failure to meet this threshold will result in study removal. Subjects may elect to withdraw from the study at any time. They will be directed to contact the study PI.
- The study PI will remove their identifiable information from study documentation. If they have completed the pre and post surveys, their de-identified data will remain in the study and will be used for analysis. If they have not completed the post-intervention survey, their data will not be used for analysis.
- An annotation will be made to the spreadsheet to indicate that the participant has withdrawn from the study.
- Participants who withdraw from the study will not be replaced. Sample size of 98 already accounts for possible attrition.
- In the event of participant withdrawal, collected data will be used in the study. Time of withdrawal and impact to study findings will be discussed in the results and study limitations. The same is reflected in the informed consent for all participants.

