5.6. Follow-up and end-of study (if applicable)

5.7. Statistical Method

5.7.1. Sample size calculation and justification

A priori power analysis was completed to guide sample size determination (Cohen, 1992). This was done to control for the potential threat to statistical conclusion validity that can occur due to low statistical power, often associated with inadequate sample size selection (Gray et al., 2017).

Based on published SDSCA data for diet and a calculated effect size of 0.41 (doi:10.1177/0145721712443292), an alpha of 0.05 and power of 0.80 for a paired two-sided test, a sample size of 49 is adequate. Assuming a 50% incompleteness rate, a sample size of 98 would be able to detect a pre- and post-survey difference at 80% power ([R version 4.3.3; `pwr.t.test`]; Cohen, 1992; Choi & Rush, 2012; Kang, 2021; Plichta & Kelvin, 2013).

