6.5.3 Estimated Amount

Demographic and DSM data will be collected for all 98 participants. The former will be collected during Week 1 and the latter, during Weeks 1 and 5.

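### Section 4.3 removes low attenders and gives opposite rules for baseline-only data; with about 50% loss planned, the estimated change can be biased

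*Combined protocol and SAP*

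**What the plan says.** Section 4.3 sets an attendance condition: "Study participants are required to participate in 80% of educational sessions. Failure to meet this threshold will result in study removal". With five sessions, 80% is four, so missing two or more leads to removal.

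The same section deals with withdrawn participants' data twice. One bullet keeps the data of those who completed both surveys, and says of the others: "If they have not completed the post-intervention survey, their data will not be used for analysis". A later bullet says: "In the event of participant withdrawal, collected data will be used in the study". That bullet also promises to discuss the timing and impact of withdrawals in the results and limitations, and says that the consent form carries the same terms. Withdrawn participants are not replaced.

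Section 5.7.1 plans for heavy loss: "Assuming a 50% incompleteness rate, a sample size of 98 would be able to detect a pre- and post-survey difference at 80% power". Section 4.2.1 repeats the figure of about 50%. Section 6.5.3, by contrast, says: "Demographic and DSM data will be collected for all 98 participants".

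Section 5.7.2 refers to complete cases only in a note on sample sizes in the summary tables. It defines no analysis set, no method for missing post-surveys, no sensitivity analysis and no comparison of completers with non-completers. The primary model for each outcome is a linear regression of the score on time, with no participant term stated.

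**The concern.** The objective and hypotheses (3.2, 3.3) concern adult Hispanic men with T2DM who receive the programme. If the men analysed are largely those who kept attending, the result describes a group selected on behaviour after baseline. Attendance is plausibly linked to motivation, and so to self-reported diet, exercise and medication use. There is no control group in which the same selection could operate and cancel.

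The conflicting rules add a second problem. For the roughly half of the sample expected to lack a post-survey, the choice of rule decides whether the baseline record enters the model, and that can change the estimate. As the plan stands, the choice could be made after the data are seen. Week 5 responses that were never sought cannot be recovered later.

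**Working it through.** **1. The plan's own figures.** Inputs from 5.7.1: "Based on published SDSCA data for diet and a calculated effect size of 0.41", and "an alpha of 0.05 and power of 0.80 for a paired two-sided test, a sample size of 49 is adequate". The exact noncentral t calculation gives power 0.803 with 49 pairs and 0.794 with 48, so 49 is the smallest adequate number. Inflating for loss, 49 / (1 − 0.5) = 98. Both figures reproduce. The inflation protects the number of pairs, but it does not make those pairs representative of the 98.

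**2. The data-use rules side by side.**

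| Participant | Earlier bullet | Later bullet |
|---|---|---|
| Withdrew, both surveys | used | used |
| Withdrew, baseline only | not used | used |
| Removed for low attendance, both surveys | unclear whether covered | unclear whether covered |

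The second row is a contradiction. The third is a gap, because the text does not say whether removal counts as withdrawal.

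**3. Complete-case reading: dilution.** Let completers change by 0.41 SD and let non-completers change by a fraction r of that (r is assumed). With half lost, the change in all enrolled is 0.5 × 0.41 + 0.5 × 0.41 × r.

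| r | All-enrolled change (SD) | Overstatement by completers |
|---|---|---|
| 1 | 0.41 | 1.0 times |
| 0.5 | 0.31 | 1.33 times |
| 0 | 0.205 | 2.0 times |

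**4. Complete-case reading: no true change overall.** Assume that the tendency to be retained and the individual change are jointly normal with correlation ρ, and that the upper half is retained. The mean change among those retained is ρ × φ(0) / 0.5 = 0.798ρ SD, and their SD is √(1 − 0.637ρ²), where 0.637 = 0.798². Rejection is for a two-sided paired t-test with 49 pairs.

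| ρ (assumed) | Spurious change (SD) | Rejection (nominal 5%) |
|---|---|---|
| 0 | 0 | 5% |
| 0.1 | 0.08 | about 9% |
| 0.2 | 0.16 | about 20% |
| 0.3 | 0.24 | about 39% |

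Simulation gave 20% and 39% for the last two rows. The planned loss matters: at ρ = 0.3 the spurious change is 0.24 SD with 50% lost, 0.15 SD with 30% lost and 0.11 SD with 20% lost. The rejection rates are for the paired test on which the sample size rests. A time-only regression on the same pairs carries the same bias but, at a positive pre-post correlation, rejects less often.

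**5. Baseline-only records kept, time-only regression.** The pre mean then covers 98 men and the post mean 49. If completers' baseline mean exceeds non-completers' by g, the mean of all 98 baselines lies 0.5g below the completers' mean. With no true change, the time coefficient is therefore biased by 0.5g, in the direction of the gap. Simulated with pre-post correlation 0.5 (assumed):

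- g = 0.5 SD: bias +0.25 SD, rejection about 23%.
- g = 0.3 SD: bias +0.15 SD, rejection about 8%.
- g = −0.5 SD: bias −0.25 SD, with rejection about as frequent but in the direction of harm.
- g = 0: no bias, rejection about 1.6%, because this model ignores the pairing.

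**The case against.** The strongest reply is that nothing in the documents shows a bias. If loss is unrelated to both baseline score and change, the bias is zero. No completer or non-completer data are given, and 50% is a planning figure, not an observed rate. Section 4.3 also undertakes to discuss withdrawals as a limitation. All of this is correct. It limits the claim to a plan that can bias, and the promised discussion is partial mitigation only, since it cannot supply outcomes that were not collected.

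Four stronger inferences are tempting, and the documents do not support them.

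- *Every reading of 4.3 favours benefit.* If completers start lower than non-completers, keeping baseline-only records biases against benefit. On complete cases the baseline gap cancels. On a 0–7 day scale, men who start high also have less room to improve.
- *Removal ends outcome collection.* That is a natural reading, but 4.3 does not say it. The bullet keeping data from men with both surveys may cover those removed, and 6.5.3 speaks of collecting data on all 98.
- *The effect is overstated two-fold, or the false-positive rate is 23%.* Two-fold is the end of a range from 1.0 to 2.0. The 23% needs three things together: the reading that the SAP's complete-case wording supports less, a regression without a participant term, and an assumed 0.5 SD gap.
- *Missing the Week 1 or Week 5 session means a missing survey.* Sections 4.4, 5.3 and 6.5.1 allow electronic completion. What is absent is a stated make-up procedure.

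**Conclusion.** The concern holds in limited form. The contradiction over baseline-only data is certain from the text, as is the absence of a defined analysis set. So is the planned loss of about half the sample without replacement. It follows that the estimate can describe a selected group, or can mix change with a shift in who is measured.

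Size and direction are conditional. Overstatement is the plausible direction on complete cases because retention is tied to attendance, but its extent rests on the assumed r or ρ. The baseline-only scenario rests on an assumed gap and correlation, and its direction follows the sign of the gap. The sample-size arithmetic is not in question.

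This should be settled before any data are analysed, and preferably while Week 5 surveys can still be sought.

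**What to change.** - Replace the two conflicting bullets in 4.3 with one data-use rule that says explicitly whether it covers participants removed for low attendance. Align the consent form with it, and reconcile 6.5.3.
- Separate attendance from outcome collection. Seek the Week 5 SDSCA-Sp from every consented participant who has not declined, whatever his attendance. REDCap already supports electronic completion. The text messages now carry the class link, and a survey link can be added.
- Define the primary analysis set in 5.7.2 as all enrolled with a baseline survey, and use a participant-level mixed model. It keeps baseline-only records and is valid if data are missing at random.
- Add a sensitivity analysis for data missing not at random, for example assuming no change in non-completers. The mixed model does not remove bias that arises because retained men change more for unobserved reasons.
- Report the set with at least 80% attendance as a further sensitivity analysis.
- Tabulate baseline scores of completers against non-completers.

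The cost is revised wording in the protocol, SAP and consent form, one more survey message and a little more analysis. The estimated change will probably be smaller. If all 98 were followed, power at the three all-enrolled effects of 0.41, 0.31 and 0.205 SD would be 0.98, 0.85 and 0.52 for a paired test.
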